### **9.1.3 Early Termination of Treatment**

If a subject prematurely discontinues study drug treatment, an ETT Visit should be scheduled as soon as possible after the decision to discontinue treatment.

If the ETT Visit occurs 3 weeks or later following the last dose of study drug, then the ETT Visit will replace the Safety Follow-up Visit, and a separate Safety Follow-up Visit will not be required.

During the course of study conduct, if local health authorities decline to approve the TC of VX-445/TEZ/IVA, or if clinical benefit is not demonstrated for the use of the TC for the treatment of CF in specific subpopulations enrolled in this study, subjects with the relevant *CFTR* genotypes may be discontinued after communication to investigators and IRBs/IECs of the risks/benefits related to the safety and efficacy observed for the relevant subset of subjects.

If a subject withdraws from the study and also withdraws consent or assent, no further assessments will be performed. Vertex may retain and continue to use any data and samples collected before such withdrawal of consent or assent.

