## 9.9 Removal of Subjects

Subjects may withdraw from the study at any time at their own request. Subjects may be withdrawn from study drug treatment at any time at the discretion of the investigator or Vertex for safety, behavior, noncompliance with study procedures, or administrative reasons.

In addition, a subject must be discontinued from study drug treatment if the subject meets any of the following criteria:

- Meets any of the stopping (discontinuation) criteria (Section 9.8)
- Becomes pregnant (Section 11.4.9.2)

If a subject does not return for a scheduled visit, reasonable effort will be made to contact the subject. In any circumstance, reasonable effort will be made to document subject outcome. The investigator will inquire about the reason for withdrawal, request that the subject return all unused investigational product(s), request that the subject return for an ETT Visit and Safety Follow-up Visit, if applicable (Section 9.1.2), and follow up with the subject regarding any unresolved AEs.

If the subject withdraws consent or assent for the study, no further assessments will be performed. Vertex may retain and continue using the study data and samples after the study ends, and may use the samples and information in the development of the study compounds, and for other drugs and diagnostics, in publications and presentations, and for education purposes. If the subject withdraws from the study, the study data and samples collected will remain part of the study. A subject will not be able to request the withdrawal of his or her information from the study data. A subject may request destruction of the samples collected from him or her during the study as long as those samples can be identified as his or her samples.

With the exception of subjects who cannot access the commercial product after regulatory approval because reimbursement by the subject's insurance carrier (whether government or private payer) is not yet available or because the subject lacks insurance coverage, subjects who become eligible to receive commercially available VX-445/TEZ/IVA by prescription of a physician may be discontinued from study drug dosing and will complete the ETT Visit before beginning commercially available VX-445/TEZ/IVA dosing. The Safety Follow-up Visit will not be required if the subject immediately continues on commercially available VX-445/TEZ/IVA.

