#### **Part A and Part B**

Duration of study drug exposure (in days) will be calculated as: last dose date of study drug in the corresponding part – first dose date of study drug in the corresponding part + 1, regardless of study drug interruption.

For subjects who enroll in another qualified Vertex study before completing this study and resume participation in this study, time spent in the other study will be excluded.

Study drug exposure (in weeks) will be summarized descriptively by the number of subjects (n), mean, SD, median, min, and max. It will also be summarized into the following categories:  $\leq 24$  weeks,  $>24-\leq 48$  weeks,  $>48-\leq 72$  weeks,  $>72-\leq 96$  weeks,  $>96$  weeks for Part A;  $\leq 24$  weeks,  $>24-\leq 48$  weeks,  $>48$  weeks for Part B.

Additionally, the total study drug exposure, defined as the sum of the study drug exposure across all subjects (in patient-weeks and patient-years), will be provided.

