1. Age (in years) at first dose date and post-baseline visit (for demographics, listing and the calculation of [percent] predicted spirometry variables):

Obtain the age at informed consent in "yy, mm" format (e.g., 24 years, 6 months) from the Vital Signs (VS) page at the Day 1 Visit and add 0.5 month to convert to days.

Obtain the informed consent date.

Then age (in years) at first dose or post-baseline visit = [(first dose date or post-baseline visit date – informed consent date) in days + age at informed consent (in days)]/365.25.

2. Missing first dose date or last dose date

If the first dose date is missing, use Day 1 visit date.

If the last dose date of study drug is not available and there is no data to indicate that the subject discontinued treatment, the data cutoff date will be used instead.

If the subject discontinued treatment and the last dose date is missing or partial date is reported, the last dose date will be imputed based on, in descending order priority, the Early Treatment Termination (ETT) visit date, last visit date before the Safety Follow-up, or the last study drug administration date from EX SDTM domain, as appropriate. The imputation algorithm will ensure the imputed last dose date does not exceed the data cutoff date.

3. Electrocardiogram:

Baseline is defined in Section 8.1. If multiple ECG measurements are obtained on the same calendar day during the TE period,

- For summary purpose, the average value will be used as the ECG on that day;
- For threshold analysis purpose, all ECG values will be used

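### For discontinued subjects with a missing or partial last-dose date, the SAP ranks the ETT visit date above the dosing record, so exposure can be overstated by the gap between last dose and ETT Visit

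*SAP*

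**What the plan says.** SAP Appendix A, Derived Variables item 2, opens the rule with "If the subject discontinued treatment and the last dose date is missing or partial date is reported". The sources are then ranked "in descending order priority, the Early Treatment Termination (ETT) visit date, last visit date before the Safety Follow-up", followed by "or the last study drug administration date from EX SDTM domain, as appropriate". One limit is given: "The imputation algorithm will ensure the imputed last dose date does not exceed the data cutoff date". Nothing says that a complete EX date overrides a later visit date, or that the result must fall in a month or year that the site did report.

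On timing, Protocol Section 9.1.3 says that "an ETT Visit should be scheduled as soon as possible after the decision to discontinue treatment". The same section provides for a long delay, in a clause that begins "If the ETT Visit occurs 3 weeks or later following the last dose of study drug": in that case the ETT Visit replaces the Safety Follow-up Visit. No upper limit on the delay is given.

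The imputed date feeds several results. SAP Section 8.2.5 counts exposure from the first dose to the "last dose date of study drug in the corresponding part", plus 1 day. Section 8.2.6 uses that duration as the denominator of compliance and, multiplied by planned tablets per day, of percentage of tablets taken. Section 8.4.1 presents exposure-adjusted event rates. Section 8.1 ends the TE Period at 28 days after the last dose or at completion of participation, whichever comes first.

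**The concern.** An ETT Visit that follows the decision to stop is an upper bound on the last dose, not an estimate of it. For some safety stops the gap is built in. Under Protocol Section 9.8.1, dosing is interrupted before confirmatory liver testing and discontinuation depends on the later result, so the last dose precedes the decision and the ETT Visit follows it.

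Read as written, the rule can replace a recorded administration date with a later visit date. It can also move a last dose reported for one month into the next. That departs from the SAP's own habit: Appendices B and C fill in only the missing part of a partial medication or AE date, apart from stated limits such as the consent or cutoff date.

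At stake is the accuracy of individual exposure and adherence for some subjects who stopped early, in a study whose primary endpoint is safety and tolerability. When an ETT Visit is used, the error runs toward longer exposure.

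**Working it through.** **The plan's own figure.** The documents give no count of missing last-dose dates and no distribution of the gap. The only quantitative statement in the plan is the zero-event bound for over 400 subjects. It reproduces (1 − 0.05^(1/400) = 0.746% one-sided, below 1%) and does not depend on this rule.

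**Assumed quantities.** Let g be the days from true last dose to ETT Visit, L the true exposure in days, and k the number of affected subjects. All three are assumptions, shown over a range. From the documents: N = 400, 96 weeks = 672 days, a 28-day TE tail, and a Safety Follow-up Visit at 28 ± 7 days.

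**1. Exposure per subject.** Imputed exposure = L + g, so the overstatement is g/L.

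| True last dose | g = 1 | g = 7 | g = 21 | g = 35 |
|---|---|---|---|---|
| Day 28 | 3.6% | 25% | 75% | 125% |
| Day 84 | 1.2% | 8.3% | 25% | 41.7% |
| Day 336 | 0.3% | 2.1% | 6.2% | 10.4% |

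**2. Adherence measures, with L = 84 and g = 21.**
- With 20 interruption days, and gap days not counted as interruption, compliance goes from 100 × (1 − 20/84) = 76.2% to 100 × (1 − 20/105) = 81.0%. This crosses the 80% cut in SAP Section 8.2.6, which is also a potential important deviation in Section 8.2.7.
- In a fully adherent subject, percentage of tablets taken goes from 100% to 100 × 84/105 = 80%; planned tablets per day cancels.

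One wrong date thus moves the two measures in opposite directions.

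**3. Pooled exposure.** Overstatement = k × g / [(400 − k) × 672 + k × 84], with affected subjects stopping on Day 84 and all others treated for 672 days.
- k = 1, g = 21: 21/268,212 = 0.008%
- k = 4, g = 21: 84/266,448 = 0.03%
- k = 20, g = 21: 420/257,040 = 0.16%
- k = 40, g = 35: 1,400/245,280 = 0.57%

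The SAP does not give the formula for the exposure-adjusted rate. If total exposure is the denominator, the rate in the last scenario is multiplied by 245,280/246,680 = 0.994. Shorter treatment in the other subjects raises the percentage: if they averaged 336 days, the last scenario gives 1,400/(360 × 336 + 40 × 84) = 1,400/124,320 = 1.1%.

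**4. TE Period.** With completion of participation C days after the true last dose, the change is min(g + 28, C) − min(28, C).
- g from 21 to 28, ETT Visit ends participation (C = g): g − g = 0.
- g above 28, ETT Visit ends participation: g − 28; for g = 35 this is 35 − 28 = 7 days.
- g below 21, with a separate Safety Follow-up Visit in its window (C from 21 to 35): 0 to 7 days.

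**The case against.** The best defence is that this is a residual fallback. Most early stoppers will have a recorded last-dose date, and Protocol Section 13.3 has missing data queried with the site. The ETT Visit is meant to follow the decision promptly, and a subject moving to commercial drug "will complete the ETT Visit before beginning commercially available VX-445/TEZ/IVA dosing", so the gap there may be about zero. The rule also ends with a qualifier that leaves room for judgement. These points limit the frequency and size of the error. They do not settle the order, because an undefined qualifier attached to a stated priority leaves the choice to undocumented programming.

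A second defence is stronger. The documents do not show what EX holds for these subjects. If the last-dose date is missing, the EX end date may be missing too, and the last complete EX record may precede the true last dose. Using it would understate exposure and could end the TE Period too soon. This stands, and it makes the fix conditional.

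Three stronger readings are tempting, and the documents do not support them:
- That exposure is overstated in early stoppers generally. The rule needs both discontinuation and a missing or partial date. Without an ETT Visit, the second-ranked source can precede the true last dose, for example in a subject lost to follow-up, and understate exposure.
- That off-drug ETT results are relabelled as on treatment. The TE Period already runs to 28 days after the last dose unless participation ends sooner, and by-visit windows count study days rather than time since last dose. An ETT Visit at day 21 falls inside the TE Period under either date; only one more than 28 days after the last dose is brought in.
- That the affected subjects carry most of the tolerability information. Protocol Section 9.9 also allows withdrawal for administrative reasons and for moving to commercial drug.

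**Conclusion.** The point holds as a minor one. For a discontinued subject with a missing or partial last-dose date, a delayed ETT Visit and a complete EX date, the stated order overstates exposure by the length of the gap. It can also place the last dose outside a reported month or year.

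For one subject the effect can be material: +25% for a Day 84 last dose and a 21-day gap, with a possible change of compliance category. For the study it is small: under about 0.6% of pooled exposure in the scenarios where the other subjects complete 672 days. Where the ETT Visit ends participation, the TE Period is lengthened only for gaps over 28 days.

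These sizes rest on assumed values of k, g and stopping day. The true number affected is unknown and could be zero. Nothing here calls the descriptive safety conclusions into question.

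**What to change.** Reword SAP Appendix A, Derived Variables item 2, before database lock:

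1. Use the last administration date in EX first, when it is a complete end date.
2. Otherwise impute from visit dates, treating the ETT date as an upper bound.
3. Require any imputed date to fall within a reported partial month or year. If only the month is known, for example, the result could not be later than the end of that month or the ETT date, whichever is earlier.
4. Define or delete the closing qualifier, and report how many last-dose dates were imputed.

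The cost is a few lines of SAP text and a small programming change, with no new data. The downside is a risk of understating exposure if an incomplete EX record were used; the completeness condition in step 1 avoids this.

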## Appendix B: Imputation Rules for Missing Prior/Concomitant Medication Dates

Imputation rules for missing or partial medication start/stop dates are defined below:

1. Missing or partial medication start date:
  - a. If only DAY is missing, use the first day of the month.
  - b. If DAY and Month are both missing, use the first day of the year.
  - c. If DAY, Month and Year are all missing, use a date before the first dose date (to impute in practical, use the informed consent date).
2. Missing or partial medication stop date:
  - a. If only DAY is missing, use the last day of the month.
  - b. If DAY and Month are both missing, use the last day of the year.
  - c. If DAY, Month and year are all missing, assign ‘continuing’ status to stop date (to impute in practical, use the End of Study Date to impute).

In summary, the prior, concomitant, or post categorization of a medication is described below.

Medication Start Date	Medication Stop Date		
	< First Dose Date of Study Drug in the Corresponding Part	≥ First Dose Date and ≤ End Date of TE Period in the Corresponding Part	> End Date of TE Period in the Corresponding Part
< First dose date of study drug in one part	P	PC	PCA
≥ First dose date and ≤ End date of TE period in one part	-	C	CA
> End date of TE period in one part	-	-	A

P: Prior; C: Concomitant; A: Post

Same imputation rule will be implemented for missing and/or partial dates of non-pharmacological treatment/procedure.

## Appendix C: Imputation Rules for Missing AE dates

Imputation rules for missing or partial AE start date are defined below. If the imputed AE start date is before the informed consent/assent date for this study, the AE start date will be imputed using the informed consent/assent date.

- **If only Day of AE start date is missing:**

- If the full (or partial) AE end date is NOT before the first dose date or AE end date is missing, then
  - if AE start year and month are equal to the month and year of first dose date, then impute the AE start day as the day of first dose date;
  - else impute the AE start day as 1.
- else impute the AE start day as 1.

- **If Day and Month of AE start date are missing:**

- If the full (or partial) AE end date is NOT before the first dose date or AE end date is missing, then
  - if AE start year is equal to the year of first dose date, then impute the AE start month and day as the month and day of first dose date;
  - else impute the AE start month as January and day as 1.
- else impute the AE start month as January and day as 1.

- **If Year of AE start date is missing:**

If the year of AE start is missing or AE start date is completely missing then query site.

- If the full (or partial) AE end date is NOT before the first dose date of the Treatment Period or AE end date is missing, then impute the AE start date as the first dose date.
- else impute the AE start date as the informed consent date.

Compare the imputed AE start date with TE period to determine whether the AE is pretreatment AE, TEAE or post-treatment AE.

Imputation rules for partial AE end date are defined below:

If partial end date, then impute as min (the last day of the month, data cut-off, end of study) if day is missing, or min (Dec, data cut-off, end of study) if month is missing.

## Appendix D: Criteria for Threshold Analysis

**Table 11-3 Threshold Analysis Criteria for Laboratory Tests (as applicable)**

Parameter	Threshold Analysis	Comments
Clinical Chemistry (LFT)		
ALT	>ULN - ≤3xULN >3x - ≤ 5xULN >5x - ≤ 8xULN >8x - ≤ 20.0xULN >20.0xULN	FDA DILI Guidance Jul 2009.
AST	>ULN - ≤3xULN >3x - ≤ 5xULN >5x - ≤ 8xULN >8x - ≤ 20.0xULN >20.0xULN	FDA DILI Guidance Jul 2009.
ALT or AST	(ALT>ULN - ≤ 3xULN) or (AST>ULN - ≤ 3xULN) (ALT>3x - ≤ 5xULN) or (AST>3x - ≤ 5xULN) (ALT>5x- ≤ 8xULN) or (AST>5x - ≤ 8xULN) (ALT>8x - ≤ 20xULN) or (AST>8x - ≤ 20xULN) ALT>20xULN or AST> 20 xULN	FDA DILI Guidance
Alkaline Phosphatase	>ULN - ≤ 1.5xULN >1.5 - ≤ 2.5 xULN >2.5 - ≤ 5.0 x ULN >5.0 - ≤ 20.0 x ULN >20.0 x ULN	FDA DILI Guidance Jul 2009.
Total Bilirubin	>ULN - ≤ 1.5xULN >1.5 - ≤ 2xULN >2 - ≤ 3xULN >3 - ≤ 10xULN >10xULN	FDA DILI Guidance Jul 2009.
Direct Bilirubin	>ULN - ≤ 1.5xULN >1.5 - ≤ 2xULN >2 - ≤ 3xULN >3 - ≤ 10xULN >10xULN	FDA DILI Guidance Jul 2009.
Indirect Bilirubin	>ULN - ≤ 1.5xULN >1.5 - ≤ 2xULN >2 - ≤ 3xULN >3 - ≤ 10xULN >10xULN	FDA DILI Guidance Jul 2009.
ALT and Total Bilirubin	ALT>3xULN and TBILI>2xULN	FDA DILI Guidance Jul 2009.

**Table 11-3 Threshold Analysis Criteria for Laboratory Tests (as applicable)**

Parameter	Threshold Analysis	Comments
AST and Total Bilirubin	AST>3xULN and TBILI>2xULN	FDA DILI Guidance Jul 2009.
(ALT or AST) and Total Bilirubin	(ALT>3xULN or AST>3xULN) and TBILI>2xULN	FDA DILI Guidance Jul 2009.
GGT	>ULN - ≤ 2.5xULN >2.5 - ≤ 5.0xULN >5.0 - ≤ 20.0xULN >20.0xULN	CTCAE grade 1-4
Clinical Chemistry (NON-LFT)		
Albumin	<LLN - ≥ 30 g/L <30 - ≥ 20 g/L <20 g/L	CTCAE grade 1-3
Amylase	>ULN - ≤ 1.5xULN >1.5x - ≤ 2xULN >2x - ≤ 5xULN >5xULN	Criteria based upon CTCAE
Creatinine	>ULN - ≤ 1.5xULN >1.5 - ≤ 3.0xULN >3.0 - ≤ 6.0xULN >6.0xULN	CTCAE grades 1-4
Lipase	>ULN - ≤ 1.5xULN >1.5x - ≤ 2xULN >2x - ≤ 5xULN >5xULN	Criteria based upon CTCAE
Total protein	<LLN >ULN	No CTCAE
Creatine Kinase	>ULN - ≤ 2.5 x ULN >2.5 - ≤ 5 x ULN >5 - ≤ 10x ULN >10 x ULN	CTCAE grades 1-4
Hematology		
Hemoglobin	Hgb decreased (anemia) <LLN - ≥ 100 g/L <100 - ≥ 80 g/L < 80 g/L	CTCAE grade 1-3
	Hgb increased >ULN - ≤ 20 g/L above ULN >20 g/L above ULN - ≤ 40 g/L above ULN >40 g/L above ULN	CTCAE grade 1-3

**Table 11-3 Threshold Analysis Criteria for Laboratory Tests (as applicable)**

Parameter	Threshold Analysis	Comments
Platelets	Platelet decreased <LLN - $\geq 75.0 \times 10^9 /L$ <75.0 - $\geq 50.0 \times 10^9 /L$ <50.0 - $\geq 25.0 \times 10^9 /L$ <25.0 $\times 10^9 /L$	CTCAE grade 1-4
	Platelet increased >ULN	No CTCAE available
Reticulocytes/Erythrocytes (%)	<LLN >ULN	No CTCAE
Coagulation		
Activated partial thromboplastin time (PTT)	>ULN - $\leq 1.5 \times ULN$ $>1.5 - \leq 2.5 \times ULN$ $>2.5 \times ULN$	CTCAE grade 1-3
Prothrombin time (PT) International Normalized Ratio (INR)	>ULN - $\leq 1.5 \times ULN$ $>1.5 - \leq 2.5 \times ULN$ $>2.5 \times ULN$	CTCAE grade 1-3

**Table 11-4 Threshold Analysis Criteria for Laboratory Tests (for labeling purpose)**

Parameter	Threshold Analysis	Comments
Clinical Chemistry (LFT)		
ALT or AST	>3xULN >5xULN >8xULN	For labeling purpose

**Table 11-5 Threshold Analysis Criteria for ECGs**

Parameter	Threshold Analysis	Comments
HR	Bradycardia <50 bpm <45 bpm Decrease from baseline $\geq 10$ bpm Decrease from baseline $\geq 20$ bpm <50 bpm and decrease from baseline $\geq 10$ bpm <50 bpm and decrease from baseline $\geq 20$ bpm	Per HV grade 2, 3, plus shift change

**Table 11-5 Threshold Analysis Criteria for ECGs**

Parameter	Threshold Analysis	Comments
	Tachycardia	Per HV grade 1, 2, 3, plus shift change
	>100 bpm >115 bpm >130 bpm Increase from baseline $\geq 10$ bpm Increase from baseline $\geq 20$ bpm >100 bpm and increase from baseline $\geq 10$ bpm >100 bpm and increase from baseline $\geq 20$ bpm	
PR	$\geq 240$ ms $\geq 300$ ms $\geq 200$ ms and increase from baseline $\geq 40$ ms $\geq 200$ ms and increase from baseline $\geq 100$ ms	
QRS	>110 ms >160 ms Increase from baseline $\geq 20$ ms Increase from baseline $\geq 40$ ms	
QTc Borderline Prolonged* Additional	>450 ms and <500ms (Male); >470 ms and <500ms (Female) $\geq 500$ ms  Increase from baseline Increase from baseline >10 ms Increase from baseline >20 ms Increase from baseline >40 ms Increase from baseline >60 ms	To be applied to any kind of QT correction formula.

Note: Based on CPMP 1997 guideline.

**Table 11-6 Threshold Analysis Criteria for Vital Signs**

Parameter	Threshold Analysis	Comments
Pulse Rate	Same as above in ECG category	
SBP increased	>140 mmHg >160 mmHg >10 mmHg increase from baseline >20 mmHg increase from baseline  >140 mmHg & >10 mmHg increase from baseline >140 mmHg & >20 mmHg increase from baseline >160 mmHg & >10 mmHg increase from baseline >160 mmHg & >20 mmHg increase from baseline	809/770 analyses
SBP decrease	<90 mmHg <80 mmHg >10 mmHg decrease from baseline >20 mmHg decrease from baseline  <90 mmHg and >10 mmHg decrease from baseline <90 mmHg and >20 mmHg decrease from baseline <80 mmHg and >10 mmHg decrease from baseline <80 mmHg and >20 mmHg decrease from baseline	Per HV grade 1, 3, plus shift change

**Table 11-6 Threshold Analysis Criteria for Vital Signs**

Parameter	Threshold Analysis	Comments	
DBP increased	>90 mmHg		
	>100 mmHg		
	>5 mmHg increase from baseline		
	>10 mmHg increase from baseline		
	>90 mmHg and >5 mmHg increase from baseline		
	>90 mmHg and >10 mmHg increase from baseline		
	>100 mmHg and >5 mmHg increase from baseline		
	>100 mmHg and >10 mmHg increase from baseline		
	DBP decreased	<60 mmHg	
		<45 mmHg	
		>5 mmHg decrease from baseline	
		>10 mmHg decrease from baseline	
		<60 mmHg and >5 mmHg decrease from baseline	
		<60 mmHg and >10 mmHg decrease from baseline	
Weight	<45 mmHg and >5 mmHg decrease from baseline		
	<45 mmHg and >10 mmHg decrease from baseline		
	<45 mmHg and >5 mmHg decrease from baseline		
	<45 mmHg and >10 mmHg decrease from baseline		
	Weight gain	CTCAE grade 1-3	
	≥5 % increase from baseline		
≥10 % increase from baseline			
≥20% increase from baseline			
Weight	Weight loss	CTCAE grade 1-3	
	≥5 % decrease from baseline		
	≥10 % decrease from baseline		
	≥20% decrease from baseline		

